4.3. Study Enrollment Procedures

Potential participants will be identified through screening OHSU's EMG lab and neuromuscular clinic patient schedules. Basic eligibility screening will be conducted using OHSU's electronic medical record database (EPIC). Patients, who pass this medical record screening will be approached by the PI. If a patient is interested, the PI will explain the objectives, risks and benefits of the study. At this point if a patient agrees to screening, the PI will proceed with an evaluation based on medical history, habits and recent (within last 2 years) EMG/NCS. The screening results will be documented using the *Subject Screening Form* (Appendix A). If a potential subject is determined to be eligible, the PI will answer all his/her questions, inform the subject that he/she may withdraw consent at any point and obtain informed consent for the study. This will involve presenting the subject with a *Lay Language Protocol Summary* and an *OHSU Consent-and-Authorization form* (as required by OHSU IRB) is also included in Appendix A.

Following enrollment, subjects will come to the lab for initial screening, consisting of QST and NCS. Following this testing, if they pass the Secondary Exclusion Criteria, subjects will be randomized to MA, LF-EA and HF-EA, using a computer-generated stratified randomization based on age and gender.

4.4. Stratified Randomization

Subjects will be randomized to the 3 intervention groups, using a specially-designed computer program which will enable stratified randomization based on 2x2 categories where one category is gender (M/F) and the other is projected median age split of 56, based on age of enrolled pilots and clinic patients with carpal tunnel syndrome (18-56/57-75).

Gender and age have confounding effect on proper estimation of NCS and QST as they vary by age and sex. Specifically, men tend to have faster nerve conduction velocities (NCV) and larger nerves than women and with age NCV declines and sensory thresholds, measured by QST tend to rise (38, 49, 55, 56). Randomization will be performed by study acupuncturist, and all outcome assessors will be blinded to it.

The randomization program is also designed to offer random order of acupuncture intervention location (median vs ulnar nerves), with a built-in ability to assign 50% of subjects within a group to median nerve first and the other 50% - to ulnar nerve first.

4.5. Accrual Plan

Subjects will be recruited from OHSU's EMG lab as the lab follows rigorous electrodiagnostic criteria for CTS diagnosis. Such criteria are usually lab-specific and take years to develop. Additionally, a recent EMG is crucial as CTS tends to fluctuate and has a relapsing-remitting course for most patients. We plan to recruit subjects in the EMG lab, immediately after completion of their NCS/EMG. The EMG lab at OHSU sees anywhere from 12-20 CTS subjects per month. Our experience with recruiting pilot subjects has been that patients are interested in the study as even 2 sessions may improve CTS symptoms and often times the alternative is more invasive such as carpal tunnel release surgery.

Of the 12-20 CTS patients seen in the lab many would not meet the eligibility criteria or would not be able to participate for reasons listed above – travel, logistics, surgery, etc. We have had great success recruiting patients local to the Portland area with mild-moderate CTS so far.

Once the protocol is approved we anticipate enrollment of 2-4 subjects per month. This number varies due to seasonal patient volume and staffing fluctuations in the EMG lab. Other factors in recruitment are: EMG lab patients who are not local to Portland and unwilling to travel for study purposes, patients who are scheduled for carpal tunnel release surgery and who wish to proceed with surgery without delay for study participation, patients who have severe carpal tunnel syndrome, rising prevalence of marijuana use (including medical marijuana), anatomic variants or other conditions making patients ineligible for the study and lastly patients who simply are not interested in participation.

An overly conservative estimation of 2 subjects per month who meet all criteria including baseline testing in the lab would translate into 24 subjects per year and a 2.5 year period of recruitment and data collection. We have capacity to test 4-5 subjects per month and will plan to do so, if we are able to recruit this number.

5. STUDY INTERVENTIONS (See Figure 1 – Study Procedures Flowchart)

5.1. Week 1 Baseline QST and NCS testing

5.1.1. Baseline QST Measurement

Patients will be tested for vibratory detection threshold (VDT) and cold detection (CDT) using the CASEIV system, described above.

VDT

Vibration Stimuli will be delivered as 25 discrete levels ranging from 0.0 to 350 micrometers (μm) of displacement, based on previously established “Just Noticeable Difference” (JND) values (38). Each stimulus is presented with an exponential onset, and turns off with an exponential decay, in order to eliminate the touch-pressure artifact, which is caused by an instantaneous on/off. Stimulation will be delivered to the 2nd digit finger pad (median distribution) and the 5th digit finger pad (ulnar distribution), with the hand stretched out supinated (palm facing up) on an even surface.

CDT

The Thermal Stimulator use a four-degree-per-second ramp up and down, and is typically operated in a range from 8 degrees to 50 degrees C., with an accuracy of 1.25 to 0.25 degrees C., depending on temperature. For high-magnitude thermal (cooling) stimuli, the absolute temperature is limited to 8 degrees C. Thermal stimuli are approximately 6 seconds in duration. CDT will be assessed over the thenar eminence (median distribution) and hypothenar eminence (ulnar distribution) with the hand on an even surface, supinated and palm facing up.

The 4, 2 and 1 stimulus presentation algorithm (to be used both for VDT and CDT)

The 4, 2, 1 stimulus presentation algorithm was developed by Dyck et al (41) as a more time-efficient alternative to forced choice, as it enables investigators to assess the sensory threshold in a given sensory modality in 2-5 minutes in most cases.

Testing will begin at an intermediate level (level 13 of 25). The stimulus will be increased (if not felt) or decreased (if felt) by four steps to the point of turnaround (felt at the higher level when not felt at lower levels, or not felt at the lower level when it had been felt at the higher level). After the first turnaround, stepping will be in steps of two. After the second turnaround, stepping will be by steps of one. A total of 20 stimulus events will be used, with five of them being randomly distributed null stimuli. If three consecutive failures are observed at level 25, testing will be terminated, and the subject will be classified as insensitive (QST hypoalgesia). If three consecutive successes were observed at level 1, testing will be terminated and the subject was classified as supersensitive (QST Hyperalgesia). Five null stimuli will be randomly interspersed among 15 non-null stimuli. A positive response (indicating perception) to more than one null stimulus will abort the program. The subject will be re-instructed, and the test will be re-run. Three failures (due to spurious answers to null stimuli) when the test is re-run twice after the test is initially aborted will indicate that the algorithm could not be used for this subject and the subject will be excluded from further participation in the study.

Following baseline QST subjects who can comply with and tolerate QST, have no hypo-or hyperalgesia will undergo baseline NCS studies.

5.1.2. Baseline Nerve Conduction Studies (NCS)

Following informed consent (obtained during subject screening), baseline nerve conduction studies will be performed according to OHSU's EMG laboratory procedures and in accordance with well established guidelines, as described by Kimura (49). These nerve conduction studies are standard clinical procedures in evaluating patients with neuromuscular diseases and will be performed using the Dantec Keypoint® G4 Workstation (Natus Medical Incorporated). Subject skin temperature will be maintained above 32 C, using a heating pad to warm up a cold hand if needed.

Specifically, the following nerve conduction studies will be performed:

a. Median Nerve Conduction Study:

We will measure the sensory nerve action potential (SNAP) amplitude from the second digit, the compound muscle action potential (CMAP) amplitudes from the Abductor Pollicis Brevis, the motor and sensory distal latency, and the nerve conduction velocity in the forearm (from the elbow to the wrist).

b. Ulnar Nerve Conduction Study:

We will measure the sensory nerve action potential (SNAP) amplitude from the fifth digit, the compound muscle action potential (CMAP) amplitudes from the Abductor Digiti Minimi, the motor and sensory distal latency, and the nerve conduction velocity in the forearm (from below elbow to the wrist)

Following baseline NCS, subjects who pass the Secondary Exclusion criteria (have mild-moderate CTS by electrodiagnostic criteria, are able to tolerate NCS, lack pure motor neuropathy or ulnar neuropathy), will be randomized as described above.

Subjects who meet the Secondary Exclusion criteria after Week 1 baseline QST and NCS testing will exit the study without being randomized and will be compensated for their time, as stated in the *OHSU Consent-and-Authorization form* (Appendix A).

5.1.3. Acupuncture Delivery (See Figure 1)

Studies will be randomized to 3 acupuncture modalities (MA, LF-EA and HF-EA). Within each group, a subject will receive 2 acupuncture sessions – one in Week 1, the other in Week 2, in random order either to the median or to the ulnar nerve. This separation into 2 sessions is necessary as there may be residual post-acupuncture effects on the first treated nerve, interfering with isolating the true effects of acupuncture on the subsequently treated nerve.

Acupuncture will be applied by an experienced licensed acupuncturist ([name] or [name]), using sterile single-use acupuncture needles (DBC Spring Ten 0.25x30 mm, 0.25x40 mm, DongBang Corp, Korea). In all 3 intervention groups, a DeQi sensation will be elicited after penetration of the skin in a depth of 3-5 mm. In the **manual acupuncture** group, a second stimulation will be given midway through the session by manual rotation/manipulation of the needles.

In the **electroacupuncture groups** (LF-EA and HF-EA) such manipulation will not be possible, however electrical stimulus intensity will be adjusted so that the subjects continues to feel the electricity-caused paresthesias/DeQi throughout the treatment period. In both electroacupuncture modalities pulse duration will be 60 microseconds, on a continuous frequency. Electroacupuncture will be performed by using an electrical device (Electrostimulator 6c.Pro, Pantheon Research, Venice, CA – **See Figs 6, 7**) with insulated cable clamps connected to the acupuncture needles.

For **LF-EA**, a frequency of 2 Hz will be used and **for HF-EA**- frequency of 100 Hz. Stimulus intensity will be increased and re-adjusted, so that the patient feels the stimulation strongly, but not painfully (2–8 mA). This will be done as each 5 minutes the patients will be asked to rate the intensity of the electrical sensation on a scale from 1-10, with desired range 6-7/10. Adjustments to stimulus intensity will be done so that it is perceived at 6-7/10 throughout the course of electroacupuncture treatment. Each acupuncture treatment will last 20 minutes.

Fig.6. Electroacupuncture delivery using Pantheon 6c Electrostimulator

Fig. 7. Pantheon 6c Pro Electrostimulator

For the median nerve acupuncture treatment (MA, LF-EA or HF-EA) the insertion points will be on the Pericardium Channel (PC3 and PC5), which are used to stimulate the channel

(Water-Metal point) according to traditional 5-element acupuncture theory (see images below). PC3 and PC5 are closely anatomically associated with the median nerve (see Figure 5).

Fig.8. Acupuncture point PC3 (Pericardium 3)

Fig.9. Acupuncture point PC5 (Pericardium 5)

For the **ulnar nerve acupuncture treatment** (MA, LF-EA or HF-EA) the insertion points will be on the Heart Channel (HT3 and HT4), which are used to stimulate the channel (water-metal points) according to traditional 5-element acupuncture theory (see images below). HT3 and HT4 are closely anatomically associated with the ulnar nerve (Figure 5).

Fig.10. Acupuncture point HT3 (Heart 3)

Fig 11. Acupuncture point HT4 (Heart 4)

5.2. Experimental Procedure Timeline (Figure 1)

During Week 1, enrolled and consented subjects will come to the lab for Week 1 Baseline QST and NCS testing as outlined above. During this baseline testing subjects will be introduced to the QST equipment and will undergo assessment of baseline cold detection threshold (CDT) and vibration detection threshold (VDT), as well as baseline NCS as outlined above. This would take approximately 1.5 hours and both procedures are non-invasive.

Following assessment of Baseline QST and NCS, subjects will be screened for Secondary Exclusion criteria, which relate to their CTS diagnosis and ability to tolerate NCS and QST (**Figure 1**). Subjects who do not pass the Secondary Exclusion Criteria will exit the study, with proper documentation of why they were ineligible.

Those who pass the Secondary Exclusion Criteria will be randomized to MA, LF-EA and HF-EA, as well as undergo random treatment assignment of median (PC3, PC5) or ulnar (HT3, HT4) nerve. Following randomization a subject will undergo acupuncture for 20 minutes involving 2 needles as outlined in detail above.

Following acupuncture, Week 1 Post-acupuncture QST (CDT and VDT) and NCS will be obtained in a manner analogous to the Week 1 Baseline QST and NCS testing outlined above. QST will be obtained first, with the needles retained in position, followed by needle removal and conduction of NCS. This will conclude Week 1. Total estimated time of Week 1 procedures is 4-4.5 hours. Subjects will be provided with water, bathroom break/other breaks as needed and a healthy snack.

Week 2 procedures will occur exactly one week after Week 1, as close to the same time of day as possible. Week 2 will start with Week 2 Baseline QST and NCS testing, following the same methodology as the Week 1 Baseline QST and NCS outlined above, although subjects will not be screened for inclusion/exclusion criteria at Week 2. A second baseline is necessary because in our experience even a single intervention to PC3, PC5 or HT3, HT4 may alter NCS and QST parameters of the median and ulnar nerves, respectively.

Once Week 2 Baseline QST and NCS testing is obtained, acupuncture will be delivered to the nerve not treated during Week 1. For example, if a given subject is randomized to LF-EA and randomly assigned to ulnar nerve acupuncture in Week 1, the same subject will be administered LF-EA to the median nerve in Week 2, following Week 2 Baseline QST and NCS (Figure 1).

After the acupuncture intervention, Week 2 Post-acupuncture QST (CDT, VDT) and NCS will be obtained in a manner analogous to those obtained in Week 1. Following completion of Week 2 NCS, subjects will complete and exit the study. Total testing time for Week 2 is estimated to be 3.5-4 hours.

Data will be recorded using the study *Data Form* (Appendix A).

5.3. Adherence Assessment

We do not anticipate problems with adherence as acupuncture will be delivered in the lab during both study visits. It is possible that some subjects will exit the study after Week 1, in which case we will include their results from Week 1 in the analysis.

6. STUDY PROCEDURE/EVALUATION SCHEDULE

Procedure	SCREENING (in EMG Lab or Neuromuscular Clinic)	WEEK 1	WEEK 2
Medical Record Screening	x		
EMG/NCS review of prior study (up to 2 yrs old)	x		
Prospective Subject Interview	x		
Study Screening by PI	x		
Screening Form	x		
Enrollment and OHSU Consent-and-Authorization Form	x		
Lay Language Protocol Summary form	x		
Baseline QST and NCS		x	x
Screening for Secondary Exclusion Criteria by PI		x	
Randomization and Random Treatment Assignment		x	
Data Form		x	x
Acupuncture Intervention		x	x
Post-acupuncture QST and NCS		x	x
Study Completion and Exit			x
Adverse Events		X	X

7. SAFETY ASSESSMENTS

Acupuncture holds the risk of minor bleeding/ecchymoses, especially in coagulopathic patients or those taking anti-platelet agents. Placing needles in the area of the median or ulnar nerves may lead to nerve damage by the needles, however the acupuncture points described above (PC3,5 and HT3,4) are commonly used and well established as safe over centuries of acupuncture practice. Furthermore, the needle used in acupuncture is 30G and solid (non-hollow), which minimizes underlying tissue damage. Electroacupuncture causes small, rapid muscle contractions surrounding the needles, which can feel unpleasant, but is not painful or harmful. In clinical practice patients routinely undergo acupuncture without any need for follow-up, unless a problem arises.

NCS testing is unpleasant to most patients, however holds no health risk. QST is widely considered safe and non-invasive.

7.1. Adverse Events and Serious Adverse Events

Assessment of acupuncture's safety is typically observation based. Adverse events typically occur as a result of treatment or in the few days immediately post-treatment. There are no lab values or other parameters, which could assure acupuncture safety.

An **adverse event (AE)** is defined as any unfavorable and unintended diagnosis, symptom, sign (including an abnormal laboratory finding), syndrome or disease which either occurs during the study, having been absent at baseline, or if present at baseline, appears to worsen. Adverse events will be recorded regardless of their relationship to the study intervention.

Examples of unanticipated adverse events involving acupuncture are: infection at the acupuncture needling site, moderate-severe bruising and bleeding at the acupuncture site, moderate-severe pain and discomfort after acupuncture, new onset of weakness or numbness, permanent worsening of carpal tunnel syndrome symptoms.

A **serious adverse event (SAE)** is defined as any untoward medical occurrence that results in death, is life threatening, requires inpatient hospitalization or results in persistent or significant disability/incapacity.

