3.3. Experimental duration and follow-up

Study procedures will be carried out over 2 consecutive weeks (see **Figure 1**). As this is a mechanistic study involving immediate effects of acupuncture on a peripheral nerve, there will be no follow up period beyond Week 2. This study employs 3 commonly practiced, well established interventions, which are considered low-risk: nerve conduction studies (NCS), quantitative sensory testing (QST) and acupuncture to the forearm. Subjects will be given all necessary follow-up contact information in case of unanticipated adverse events, as described in Section 7 (Safety Assessments).

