7.2. Subject Follow up and Protection against Risk

All subjects will be given [name] contact number and encouraged to report any concerns and complications during the 8-day study period and following completion of the study. In the unlikely event that acupuncture causes lasting discomfort, bothersome ecchymoses, worsening of carpal tunnel and neuropathy symptoms, [name] will be available for urgent assessment and treatment. If the patient needs further neurologic or other care, they will be referred to [name] clinic or to one of the other providers in the neuromuscular division or another appropriate clinician within OHSU. The informed consent will clearly state that a subject may discontinue participation in the study at any time.

As with all human subject investigations at OHSU, any adverse events will be reported to the IRB and there is a Data and Safety Monitoring Plan in place (see details below).

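### No scheduled adverse-event check follows the second acupuncture session, although the plan expects events in the days after treatment; spontaneous reports alone cover that window

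*Combined protocol and SAP*

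**What the plan says.** Section 7.1 gives the expected timing of harm: "Adverse events typically occur as a result of treatment or in the few days immediately post-treatment". It describes safety assessment of acupuncture as resting on observation, with no laboratory value or other parameter to stand in for it. It commits the study to recording events whether or not they are related to the intervention. Its definition covers an event "which either occurs during the study, having been absent at baseline, or if present at baseline, appears to worsen", with no end day.

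Four other places set the follow-up:

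- Section 3.3: "there will be no follow up period beyond Week 2". The reasons given are that the study concerns immediate effects and that its procedures are low-risk. The same section adds: "Subjects will be given all necessary follow-up contact information in case of unanticipated adverse events".
- Section 5.2: "Week 2 procedures will occur exactly one week after Week 1", and later "Following completion of Week 2 NCS, subjects will complete and exit the study".
- Section 6: the "Adverse Events" row is marked at Week 1 and Week 2, and the schedule has no later column.
- Section 7.2: subjects receive a contact number and are "encouraged to report any concerns and complications during the 8-day study period and following completion of the study". Urgent assessment is available if a problem arises.

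**The concern.** The plan names a risk window that runs a few days past each session, but it schedules an assessment inside or after that window for the first session only. The second session is followed by same-day measurements and exit.

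Sections 7.1 and 7.3 list needle-site infection, new numbness or weakness, and lasting deterioration of carpal tunnel symptoms among the reportable events. Infection would seldom be visible within hours of needling, and nerve symptoms may appear after the subject has gone home. Section 7 itself acknowledges that needling near the median and ulnar nerves can injure them. Because the plan relies on observation to detect harm, whether anyone asks matters. The independent monitor's monthly report can contain only what has been ascertained.

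A second gap concerns what happens to a late report. With a definition tied to the study period and no end day, staff could reasonably either record or leave out an event reported two days after exit. Appendix A does not settle this: its contents list names no adverse-event form, and the Data Form has no field for adverse events.

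**Working it through.** **Inputs**

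- Sessions per subject: 2 (Section 5.1.3).
- Interval between sessions: 7 days (Section 5.2).
- Exit: same visit as session 2, after the nerve conduction studies (Section 5.2).
- Scheduled adverse-event assessments: Week 1 and Week 2 visits (Section 6).
- Planned completers: 60 (Section 9.1).
- Stated study period: 8 days (Section 7.2).

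**Step 1: reproduce the plan's own figure.** Put session 1 on day 1. Session 2 falls on day 1 + 7 = 8, and exit is also on day 8. The period is 8 − 1 + 1 = 8 days inclusive, which agrees with Section 7.2.

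**Step 2: scheduled observation after each session.**

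| Session | Day | Last scheduled assessment | Days of scheduled observation after the session |
|---|---|---|---|
| 1 | 1 | Day 8 | 8 − 1 = 7 |
| 2 | 8 | Day 8 | 8 − 8 = 0 |

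Seven days covers a window of a few days on any ordinary reading. Zero days does not.

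**Step 3: share of sessions affected.** Total sessions among completers: 60 × 2 = 120. Sessions with no scheduled assessment after the session day: 60 × 1 = 60. Share: 60 / 120 = 50%. This counts completers only. A subject who leaves after Week 1 would also have no later scheduled assessment.

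**Step 4: what covers the gap.** Sections 3.3 and 7.2 provide a contact route and invite reports after completion. Section 7.3 requires adverse events to be passed on and states no cut-off at exit. Ascertainment after session 2 is therefore passive, not absent.

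**Step 5: effect of adding one contact.** Assume one scheduled contact after session 2, at an interval the documents do not give. Sessions followed by a later scheduled assessment rise from 60 of 120 (50%) to 120 of 120 (100%). Sample size and power do not change.

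**The case against.** The strongest defence is that the short follow-up is deliberate and explained. This is a mechanistic study of immediate effects using procedures the plan regards as low-risk. Section 7 notes that follow-up is not routine in acupuncture practice unless a problem arises. Safety is not one of the three aims. Same-day sensory testing and nerve conduction studies of both nerves give some check on acute nerve injury, and bleeding or pain can be seen at the session. An independent monitor is in place. The consent text was not available for this check and the monitoring plan is only summarised, so either might contain further instructions, although Section 6 shows no later contact.

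Much of this stands, and it limits the point. It does not remove it. The interest in immediate effects justifies when the outcomes are measured. It does not explain a scheduled safety window shorter than the one Section 7.1 describes.

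A reader might go further and infer that collection stops at Week 2 and that later events are not sought at all. Section 7.2 contradicts that, because it asks subjects to report after completion.

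A reader might also infer that fewer events will be counted for Week 2 than for Week 1. The documents do not establish this. Section 5.2 describes the Week 2 visit without an explicit question about events since session 1. If events were tallied by visit, Week 2 could show more of them, since it can pick up delayed events from session 1 together with immediate events from session 2. No planned analysis compares events by week.

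**Conclusion.** The point holds in a limited form. After session 2 there is no scheduled adverse-event assessment in the window the plan itself names. Spontaneous reports alone cover it, and their status as study adverse events is undefined. This applies to 60 of 120 sessions (50%), assuming 60 completers with two sessions each.

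The consequence is possible under-ascertainment of delayed second-session events. Its size is unknown and could be close to nil, because the documents give neither an event rate nor a rate of self-reporting. Someone might want to turn the 50% into a percentage undercount. That would require an assumed self-report share, equal delayed-event rates in the two sessions, and complete detection by questioning at Week 2, and the documents support none of these.

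All three arms follow the same schedule and the order of nerves is balanced within groups, so comparisons between arms should not be biased by this. The efficacy analysis is untouched. What is at stake is the completeness of the safety record.

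**What to change.** Reconcile Sections 3.3, 6, 7.1 and 7.2 as follows:

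1. Have existing staff send or make one scripted phone or e-mail adverse-event query to every subject a few days after session 2.
2. Ask the same script at the start of the Week 2 visit, so that both sessions are assessed in the same way.
3. Add the contact to the Section 6 schedule.
4. State the adverse-event collection window, and say that reports received after exit but within it are recorded as study adverse events.

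The cost is about 60 short contacts, one added schedule entry and a slightly longer time in study for each subject. No visit is added. One limit remains: a contact a few days after treatment can detect worsening but cannot show whether it is permanent.
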